4.1.2 Phase 2 Dose expansion

Patients with tumors demonstrating favorable PK and PD will proceed to Phase 2 Dose Expansion. In Dose Levels 1-3, patients will continue treatment with the same treatment level as given in Phase 0, patients should take the treatment continuously in 28d cycles with 3 weeks on / 1 week off after surgery. In Dose Level 4+, patients should take everolimus in one dose weekly; ribociclib will be taken for 21 consecutive days followed by 1 rest week. The dose will be per Table 7. If more than one DLT is observed in 6 patients in the Phase 2 dose expansion, the enrollment will be stopped and the previous lower dose level will be considered the RP2D and will be given for the remaining patients enrolled. If more than one DLT is occurred with the Level 0, the study will be stopped due to toxicity. Typically DLTs are defined by 1 cycle of treatment, which is 28 days. Since Phase 0 treatment is given for only 5 days, Phase 0 dose escalation will only be determined by Phase 0 DLT rules unless determined otherwise by the DSMB. Patients will be treated until unacceptable toxicity is observed, or until disease progression as assessed by radiographic or clinical metrics. Preliminary rates of progression-free survival in patients with high-grade gliomas treated with ribociclib+everolimus will be measured through radiographic and clinical response metrics, specifically Response Assessment in Neuro-Oncology (RANO) criteria and investigator discretion. Phase 2 participants will return to the clinic to monitor safety per the schedule of events until treatment is ended and will then be contacted approximately every 3 months by letter or phone for collection of survival data. The start of follow up for long-term survival begins following completion of the Day 30 safety follow up call.. All Phase 0/2 participants will be followed for survival for up to 5 years.

Common Toxicity Criteria Adverse Event (CTC AE 4.03) will be utilized to review ribociclib+everolimus treatment effects in patients with brain tumors.

Trough steady-state blood samples will be obtained on days 1, 8, 15, and 22 of cycles 1 and 2 prior to the administration of ribociclib+everolimus on that day. Note: ribociclib+everolimus will be administered in the clinics on the clinic visit days to ensure the collection of trough level samples.

PHASE 2 STUDY				
	Cycle 1 (28 d)	Cycle 2 (28d)	Subsequent cycles (28d)	End of study
Day of cycle	D1, D8, D15, D22	D1, D8, D15, D22	N/A	N/A

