Blood	Trough level*	Trough level*	N/A	N/A

* Trough blood sample is collected prior to the drug administration on that day. Ribociclib is administered in the clinics on the clinic visit days.

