6.1 Protocol treatment

For this protocol, the term “treatment” refers to ribociclib+everolimus.

Table 6 Dose and treatment schedule

Study treatments	Pharmaceutical form and route of administration	Dosage Form and Strength	Frequency and/or Regimen
Phase 0			(5 day regimen)
Ribociclib (LEE011)	Tablet for oral use	200mg tablets 2.5mg tablet	Once daily
Everolimus	Tablet for oral use		Once daily or Twice daily*
Phase 2 (optional)			(28 day cycle)
Ribociclib (LEE011)	Tablet for oral use	200mg tablets 2.5mg tablet	Once daily for 3 weeks, 1 week off
Everolimus	Tablet for oral use		Once daily* or Twice daily** for 3 weeks, 1 week off

*Dose Level 4+: everolimus is taken once on Day 5 in Phase 0. In Phase 2, everolimus dose will be given weekly on Days 1, 8, 15, 22 of each cycle.

**Dose Level 3: everolimus is taken twice daily in Phase 2.

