6.1.4.2 Additional Dosing Guidelines for Pharmacokinetic Sampling / ECG / Chemistry panel / Lipid Panel Collection

On days with PK, ECG sampling, chemistry panel and/or lipid panel sampling, the following additional guidelines should be followed:

- On a day when PK blood collection is scheduled at the clinic, patients must take study treatment in the clinic under the supervision of the Investigator or designee. On all other days, patients may take the study treatment at home.
- On a day of chemistry panel and/or lipid panel sampling, patients should be fasting from food and drink for at least 8 hours overnight; however, it will not be considered a deviation if the patient is not fasting. Water is allowed during all fasting periods; however, coffee, tea and juice are not permitted during the fasting period. Patients must also take study treatment in the clinic under the supervision of the Investigator or designee. On all other days, patients may take the study treatment at home.
- Pre-dose samples should be drawn prior to dosing. The sampling time of the PK samples and the dosing time must be precisely recorded in the CRF. Furthermore, the dosing date and time the study medication was taken on the day before the PK assessment must be precisely recorded in the CRF.
- Post-dose PK samples should be collected after dosing of the study treatment and precisely recorded in the CRF.
- If a pre-dose PK sample should be obtained, then the sample should be collected after the ECG and before dosing of the study treatment when possible; or allow approximately 30 minutes after the sample is drawn before obtaining the ECG.

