ECG (12-Lead)	X ²	X ^{2,4}		X ⁴	X ⁴	X	15 ⁵	1,15 ⁵	1 ^{5,6}	X	

Initial Version date: 10/16/2018

Revision date: 03/11/2019, 5/07/2019, 09/26/2019, 03/17/2020, 08/26/2024

	PHASE 0						PHASE 2					Survival Follow Up Call/Letter
	Screening/ Baseline	Enrollment	At Home	Pre- surgical assess- ment	Craniotomy for resection tumor resection	Phase 0 Follow - Up	Cycle 1 (28d)	Cycle 2 (28d)	Subsequent cycles (28d)	End of study treat- ment (EoT)	Safety Follow- up (phone)	
Visit Number	1	2	n/a	3	4	5	6-9	10-13	14, 15,...	Last		
Day of cycle	-28 to-1	Day 1	Day 2 & 3	Day 4	Cohort 1&2 Day 5 or Cohort 3 Day 6	Post- Operative Visit	Day of Cycle	Day of Cycle	Day of Cycle	Last	30 days after last dose	~every 3 months after safety phone call
Vital signs	X ²					X	1, 15	1, 15	1	X		
Adverse events			Continuous		first study drug administration up to 30 days after last dose of study treatment					X		
Laboratory assessments												
Hematology (CBC w/Diff)		X		X ⁷		X	15	1, 15	1	X		
Chemistry (CMP, Mg+, Phos)		X ²		X ⁷		X	15	1, 15	1	X		
eGFR ³		X ²		X ⁷								
Coagulation (PT/INR, PTT)		X ²		X ⁷								
Lipid panel		X ²								1 ⁸		
Urinalysis (dipstick) with microscopic analysis		X ²					15	1	1			
Pregnancy test (serum HCG) if applicable		X ²										
Pregnancy test (urine) if applicable						X	1	1	1	X		
Study Drug												
Drug administration		X ⁹	X ⁹	X ⁹	X ⁹		Daily Days 1-28 day cycle ¹⁰					
Review of Home Dosing Diary and Symptom Diary				X			1	1	1	X		
PK & Biomarker sample collections												
PK Blood Sampling		X		X ¹¹	X ¹¹		1, 8, 15, 22 10	1, 8, 15, 22 10				
Collection of PK CSF					X							
Collection of PK/PD Tumor tissue					X					X ¹²		
Biomarker blood collection		X ²										

1 | The most recent MRI scan available should be utilized.

	PHASE 0						PHASE 2					Survival Follow Up Call/Letter
	Screening/ Baseline	Enrollment	At Home	Pre-surgical assessment	Craniotomy for resection tumor resection	Phase 0	Cycle 1	Cycle 2	Subsequent cycles	End of study treatment (EoT)	Safety Follow-up (phone)	
Visit Number	1	2	n/a	3	4	5	6-9	10-13	14, 15,...	Last		
Day of cycle	-28 to-1	Day 1	Day 2 & 3	Day 4	Cohort 1&2 Day 5 or Cohort 3 Day 6	Post-Operative Visit	Day of Cycle	Day of Cycle	Day of Cycle	Last	30 days after last dose	~every 3 months after safety phone call

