2	Screening assessment may be completed at Day 1 predose, if completed at screening, does not need to be repeated at Day 1 pre-dose except for ECG and ECOG. Results must be available to confirm eligibility prior to dosing.											
3	Estimated glomerular filtration rate (eGFR)											
4	ECG Day 1 Pre-dose, Day 1: 2-4 hrs post-dose, and pre-surgical assessment (can be completed on Day 4 or Day 5 (Cohort 1&2) / Day 6 (Cohort 3)).											
5	ECG Pre-dose and 2-4 hours post dose on C1D15, C2D15, C3D1, C6D1; C9D1; and every 3 rd cycle...											
6	ECG Pre-dose C2D1, C4D1, C5D1; C7D1, C8D1, C10D1, C11D1; and every 1st and 2nd cycle...											
7	Performed at pre-surgical assessment as per SOC on Day 4 (can be completed on Day 5 (Cohort 1&2) or Day 6 (Cohort 3)).											
8	Lipid panel performed every 4th cycle D1											
9	Study drugs are administered in the clinics on D1, D4 and D5. Patients may take medications at home on D2 and D3											
10	Trough blood sample is collected prior to the drug administration on that day. Study drugs are administered in the clinics on the clinic visit days 1, 8, 15, 22.											
11	Blood samples will be obtained on Day 4 (the day before the surgery for Cohorts 1 & 2; 2 days before surgery for Cohort 3) at pre-dosing (trough level), 0.5, 1, 2, 4, 7 hours post dose (\pm 5 min window for 0.5hr and 1hr; \pm 15min window for 2, 4, 7hr samples). A pre-dosing (trough level) blood sample will also be obtained on Day 5 and a sample will be collected intra-operatively. In Dose Level 4+ only, PK blood sampling will occur at the same timepoints (pre, 0.5, 1, 2, 4, 6, 8 and 24) but will be obtained on Day 5 (the day of surgery); the 24 hour sample will be obtained on Day 6.											
12	Only Patients that have a recurrence and undergo an additional surgery for tumor resection											
13	The start of follow up for long-term survival begins following completion of the Day 30 safety follow up call. Subjects will continue to be followed until death or withdrawal of consent for the collection and reporting of data or lost to follow-up for up to 5 years. Public records may be used to collect survival data, i.e., obituary notices and public database searches for survival information.											

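### Phase 2 ribociclib (all levels) and everolimus (Levels 0-3) stop after Day 21, but Section 4.1.2 and Table 13 note 10 direct that study drug be given on Day 22 of Cycles 1 and 2

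*Combined protocol and SAP*

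**What the plan says.** **The regimen.** Table 6 (Section 6.1) gives Phase 2 ribociclib as "Once daily for 3 weeks, 1 week off", and puts everolimus on the same three-weeks-on, one-week-off pattern unless a footnote changes it. Section 6.1.4.1 repeats 21 days on and one rest week for both drugs at Levels 0-2. Section 4.1.2 does the same for Levels 1-3, and for Level 4 and above says "ribociclib will be taken for 21 consecutive days followed by 1 rest week". Table 7 note e and Section 6.5.3.1 agree on 21 daily ribociclib doses. The one exception is everolimus at Levels 4-6, which is weekly on Days 1, 8, 15 and 22 (Table 6 footnote, Table 7 note e).

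**The visit instructions.** Section 4.1.2 has trough steady-state blood samples "obtained on days 1, 8, 15, and 22 of cycles 1 and 2 prior to the administration of ribociclib+everolimus on that day". The footnote to the sampling table there, whose listed days include Day 22, says "Ribociclib is administered in the clinics on the clinic visit days". Section 6.1.4.2 adds: "On a day when PK blood collection is scheduled at the clinic, patients must take study treatment in the clinic". Table 13 note 10 says "Study drugs are administered in the clinics on the clinic visit days 1, 8, 15, 22". The Phase 2 drug row of Table 13 reads "Daily Days 1-28 day cycle" and shows no rest week.

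**Recording.** Section 6.1.4.2 requires sample and dose times on the sampling day, and that "the dosing date and time the study medication was taken on the day before the PK assessment must be precisely recorded in the CRF".

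**The concern.** The regimen sections and the visit instructions give a site two incompatible directions for the same day. A site working from Table 13 gives ribociclib on Day 22. A site working from Table 6 does not. Each can point to protocol text, and each could be recorded as deviating from the other. In Cycle 1 the extra dose falls inside the 28-day Phase 2 DLT window (Section 6.1.3), and in both cycles it departs from the 21-dose description in Section 6.5.3.1.

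There is also a smaller pharmacokinetic consequence. Systemic Phase 2 PK is a secondary objective (Sections 3 and 9.6). The Phase 2 samples are all labelled as steady-state troughs, but under 21 days on and 7 off they do not all follow a dose by the same interval. The recording rule reaches back only to the previous day, and Section 9.7 has no rule for handling Phase 2 samples by time since last dose.

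**Working it through.** The plan states no figure to reproduce; the check is a day count.

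**1. Is drug due on Day 22?** Three weeks on is Days 1-21, so the rest week is Days 22-28.

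| Drug and level | Due on Day 22 under the regimen? | Day 22 dose directed by 4.1.2 and note 10? |
|---|---|---|
| Ribociclib, Levels 0-6 | No | Yes |
| Everolimus, Levels 0-3 | No | Yes |
| Everolimus, Levels 4-6 | Yes (weekly) | Yes, consistent |

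**2. Size of one extra dosing day.** 22/21 − 1 = 4.8%.

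| Drug, daily dose | 21 days | With Day 22 |
|---|---|---|
| Ribociclib 400 mg (Level 0) | 8,400 mg | 8,800 mg |
| Ribociclib 600 mg (Levels 1-6) | 12,600 mg | 13,200 mg |
| Everolimus 2.5 mg (Levels 0-1) | 52.5 mg | 55 mg |
| Everolimus 5 mg (Level 2) | 105 mg | 110 mg |
| Everolimus 10 mg as 5 mg twice daily (Level 3) | 210 mg | 215 mg if only the clinic dose is taken (+2.4%); 220 mg if both are taken (+4.8%) |

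Day 22 sampling visits exist only in Cycles 1 and 2, so the excess is at most one dosing day in each of those two cycles.

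**3. Visit window (Section 7.1).** Cycle 1 allows ±1 day, so the Day 22 visit may fall on Days 21-23; two of the three are rest days. Cycle 2 allows ±3 days, so it may fall on Days 19-25; four of the seven are rest days. The nominal day is a rest day in both.

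**4. Time since the last dose under 21 on, 7 off.** For a once-daily drug last taken on Day 21:
- Day 22: 1 × 24 = 24 h, a valid trough.
- Day 23, the latest permitted in Cycle 1: 2 × 24 = 48 h.
- Day 25, the latest permitted in Cycle 2: 4 × 24 = 96 h.
- Cycle 2 Day 1, which is Day 29 counted from Cycle 1 Day 1: 8 × 24 = 192 h.

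For Level 3 everolimus, with a second Day 21 dose about 12 h after the first, the Day 22, 23 and 25 intervals are about 12, 36 and 84 h. For everolimus at Levels 4-6 the dose before a Day 22 sample is Day 15, so that sample is a 7-day trough. The Cycle 1 Day 1 sample precedes any Phase 2 dose.

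**5. Does the recording rule capture these intervals?** It covers the dose taken on the day before sampling. For samples on Days 23-25 and on Cycle 2 Day 1, the day before is a rest day for ribociclib and for everolimus at Levels 0-3, so the rule does not capture the Day 21 dose.

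**The case against.** The best reply is that the regimen itself is not in doubt. Every operative dosing statement gives ribociclib for 21 days, and the conflicting lines are sampling logistics meant to secure a pre-dose draw. The footnote in Section 4.1.2 and the rule in Section 6.1.4.2 mainly fix where a dose is taken, so they create the conflict only by implication. The days in note 10 are exactly the weekly everolimus days at Levels 4-6. Section 7.1 keeps visits going when drug is withheld, so a visit without a dose is acceptable. The window lets a site use Day 21. The dosing diary, reviewed on Day 1 of each Phase 2 cycle, may recover the Day 21 dose.

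Much of this stands, and it limits the weight of the point. It does not remove the conflict. Note 10 speaks of study drugs and names no level, and the Section 4.1.2 sentence names both drugs. No text gives one section precedence, and Section 2.3 still speaks of continuous ribociclib dosing. The window avoids the problem only for sites that choose Day 21 or earlier. The documents do not say that the diary records clock times.

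Three stronger readings are tempting and are not supported:
- The Table 13 drug row could be taken to order 28 daily doses. Its wording reads as shorthand for a 28-day cycle, and the regimen sections contradict 28 doses. It needs clarifying but adds nothing to the size.
- Because the extra dose falls in the Cycle 1 DLT window, a reader might infer a distorted recommended Phase 2 dose. The documents offer no basis for saying that one added dosing day changes a DLT count, and Section 4.1.2 rests Phase 0 escalation on Phase 0 DLTs unless the DSMB decides otherwise.
- The Day 22 sample might be thought invalid. Drawn on the nominal day before any dose, it is a proper trough for the Day 21 dose; the error lies in directing a dose after it.

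**Conclusion.** The contradiction is real and should be fixed. On the nominal Day 22 of Cycles 1 and 2, the visit instructions direct ribociclib at every level, and everolimus at Levels 0-3, on a day when the regimen gives neither. The excess is one dosing day per affected cycle, +4.8%; for Level 3 everolimus it is +2.4% if only one 5 mg dose is taken. These sizes assume full dosing on Days 1-21 and a site that follows note 10 on Day 22 itself. The PK consequence is confined to a descriptive secondary objective. It concerns the Cycle 1 Day 1 sample, the Cycle 2 Day 1 sample and samples drawn on Days 23-25, none of which is a steady-state 24 h trough under the stated regimen. Correcting the dosing instruction alone would not resolve that part.

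**What to change.** - **Section 4.1.2 (text and footnote), Section 6.1.4.2 and Table 13 note 10:** state that on Day 22 no ribociclib is given at any level and no everolimus at Levels 0-3. Only Levels 4-6 receive the weekly everolimus dose, after the sample.
- **Same places:** define the Day 22 sample as the trough after the Day 21 dose for ribociclib (all levels) and everolimus (Levels 0-3), and as the 7-day trough after the Day 15 dose for everolimus at Levels 4-6. A single definition for both drugs at all levels would be wrong.
- **Table 13 drug row:** ribociclib Days 1-21; everolimus Days 1-21 at Levels 0-3, or Days 1, 8, 15 and 22 at Levels 4-6.
- **Section 6.1.4.2:** record the date and time of the last dose of each drug taken, whichever day that was.
- **Section 9.7:** analyse Phase 2 samples by time since last dose. Do not pool as steady-state 24 h troughs the Cycle 1 Day 1 sample, the Cycle 2 Day 1 sample (about 192 h after the Day 21 dose) or in-window samples from Days 23-25.

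The cost is an amendment to the wording, the visit table and one recorded dose time. No patients, visits or samples are added.

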7.1.1 List of Efficacy/Pharmacokinetic/Pharmacodynamics and Pharmacometabolomics Measurements

7.1.1.1 Pharmacokinetic (PK) Measurements

Sample collection and processing: All patients will donate approximately a total of nine 6 mL blood samples (approximately 48ml of blood) the day before the surgery and during the surgery as noted in Table 13. If intravenous vein (IV) blood collection utilized, the approximate total volume of blood will be 58mL of blood. See the Ivy Brain Tumor Center Laboratory Manual for details regarding collection, processing, packaging and shipment.

PK sample analysis: The total and unbound concentrations of ribociclib and its active metabolite, LEQ803, in plasma, CSF, and tumor tissues (including contrast-enhancing and non-enhancing regions) will be determined by a validated LC-MS/MS method as described previously by us ([Bao X, J Pharmaceutical and Biomedical Analysis, 2019](#)). The total and unbound concentrations of everolimus in whole blood, CSF, and tumor tissues (including contrast-enhancing and non-enhancing regions) will be determined by a validated LC-MS/MS method. All analyses will be performed at the KCI Pharmacology Core Laboratory.

7.1.1.2 Pharmacometabolomics

Rationale: Novel metabolomics technologies allow high-throughput assessment of a large number of endogenous metabolites, which provide powerful tools for mapping biochemical pathways implicated in disease and in response to drug treatment. Pharmacometabolomics is an emerging field that applies metabolomics to define metabolic signature of drug exposure, thereby enabling identification of biochemical pathways implicated in drug efficacy and adverse drug reactions. By defining metabolite profiles both at baseline (prior to) and post drug exposure, pharmacometabolomics has the potential to provide early insights into mechanism of drug action and molecular basis for variation in drug response.

The plasma metabolic signatures of ribociclib plus everolimus exposure in patients will be defined using a LC-MS/MS based targeted metabolomics platform, which has been established in the Karmanos Cancer Institute Pharmacology Core ([Bao X, J Clin Pharm, 2019](#)).

We will identify the plasma metabolites that are significantly altered by ribociclib and everolimus exposure, which may provide insights into the mechanism of drug action. In addition, we will explore the associations between the metabolite changes and PK/PD parameters, toxicity, or clinical response. This may help identify potential metabolic biomarkers for the early prediction of clinical outcome.

Pharmacometabolomic samples: No extra sample collection is required for pharmacometabolomic study. Metabolomic profiling will be performed using the plasma PK samples collected at pretreatment and following the combination therapy at 2, 7, and 24 h.

LC-MS/MS based targeted metabolomics: Metabolites in plasma samples will be quantitatively profiled using a LC-MS/MS based targeted metabolomics platform in the Karmanos Cancer

Institute Pharmacology Core, as described previously ([Bao X, J Clin Pharm, 2019](#)). This platform can quantitatively measure about ~250 metabolites that are involved in major human metabolic pathways. All LC-MS/MS analyses were performed on an AB SCIEX QTRAP 6500 LC-MS/MS system. Analyst® 1.6 software was used for system control and data acquisition and MultiQuant 3.0 software was used for data processing and quantitation.

Metabolomic data analysis: Metabolomics data analyses were performed using the MetaboAnalyst web-based statistical package (<http://www.metaboanalyst.ca/>). Features (i.e., Metabolites) with >50% missing values were removed from the analysis, and the remaining missing values were replaced by the minimum value of a feature. To meet the normality assumption, individual metabolite concentrations were log-transformed and then auto-scaled (mean-centered and divided by the standard deviation of each metabolite). A one-way analysis of variance (ANOVA), if significant, followed by Fisher's LSD post-hoc analysis was performed to identify significantly changed metabolites among groups. The study of metabolic signature of the drug exposure in patients was intended to be hypothesis-generating and thus a false discovery rate (FDR) adjusted p-value < 0.2 along with unadjusted p-value < 0.05 was used to identify plasma metabolites significantly changed. A heat map was used to visualize metabolic signatures of ribociclib plus everolimus exposure, with significantly changed metabolites ranked in ascending order according to the FDR adjusted p-values from the ANOVA test.

